## 8 Summary of Study Data

Information on continuous variables will be given as means and standard deviations.

Categorical variables will be summarized as frequencies or percentages of observed levels.

### 8.1 Subject Disposition

Flow of study subjects.

## 8.2 Protocol Deviations

Protocol deviations that influence the analysis and consequences:

- Not fulfilling inclusion criteria ○ Subjects will not be included in the full analysis population
- Withdrawal of consent ○ Subjects will not be included in the full analysis population
- Withdrawal of consent to read medical file ○ Subjects will not be included in the full analysis population
- Drop-out for other reasons ○ Subjects will not be included in the full analysis population
- Single missing values ○ Subjects will be included in the full analysis population

## 8.3 Clinical Investigation Plan Deviations

Data will be analyzed according to the Statistical Analysis Plan; any further/additional/deviation from the Statistical Analysis Plan will be reported as such.

## 8.4 Baseline Variables

- Age
- Gender
- Affected leg/examined leg
- Risk factors for PAD (smoking, arterial hypertension, lipid abnormalities, diabetes mellitus, obesity, positive family history)
- Relevant underlying diseases (CHD, CHF, atrial fibrillation, CKD, carotid artery stenosis, previous cerebrovascular event)
- Previous surgery or interventions on the arterial vessels of the lower extremity
- Current medication
- Date of last angiography

## 9 Diagnostic Performance Analysis

The distribution of single MSOT readouts after exercise and the distribution of difference values of the MSOT readouts after and before exercise will be assessed and statistically tested as possible criteria to determine PAD affected legs.

## 9.1 Correlations

The association and correlation, respectively, of MSOT parameters versus clinical/angiographic outcomes (secondary endpoints) is calculated by appropriate measures of association and correlation, e.g. differences in mean, or Pearson's or Spearman's rank correlation coefficients.

## 9.2 Sensitivity and Specificity

Using the cutpoint maximising the Youden index derived from study group 1 based on healthy volunteers vs. IC patients, the diagnostic properties of MSOT values will be illustrated by sensitivity and specificity (with 95% confidence interval) associated with a diagnostic test decision dichotomised at that cutpoint. The same cutpoint will be employed in study group 2 for validation of diagnostic properties.

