- Subgroup analysis: The reperfusion profiles of MSOT parameters measured again after revascularization intervention show tendencies towards the reperfusion profiles of healthy subjects compared to the measurements before intervention

Primary objectives:

- Study group 1: Derivation of optimal diagnostic MSOT threshold values regarding oxygenated hemoglobin after exercise in claudication patients and a healthy control group
- Study group 2: Validation of the diagnostic accuracy of MSOT, employing the cut-off values derived in study group 1, regarding oxygenated hemoglobin after exercise in claudication patients and a healthy control group in an independent cohort

Secondary objectives:

- Recording of all other hemoglobin-associated parameters in the calf muscle before and after repetitive heel raises using MSOT
- Recording of the reperfusion profiles (i.e. the curves of hemoglobin-associated parameters in the first ten minutes after exercise) and determination of general characteristics of the curves to distinguish between PAD legs and healthy legs
- Recording of the flow profiles and PSVs of the A. femoralis communis and A. poplitea using CCDS and correlation with the collected MSOT parameters
- Recording of the ABI and correlation with the collected MSOT parameters
- Recording of the relative (until the first occurrence of pain) and absolute walking distance (until the first stopping due to pain) and correlation with the collected MSOT parameters
- Recording of the maximum walking distance in the 6MWT and correlation with the collected MSOT parameters
- Recording of the subjectively perceived maximum walking distance in everyday life and correlation with the collected MSOT parameters
- Recording of the perceived PAD-specific quality of life (VASCUQOL-6 questionnaire) and correlation with the collected MSOT parameters

- Recording of the radiological degree of severity and correlation with the collected MSOT parameters
[If angiographic imaging is already available due to routine diagnostics independently from this study.]
- Subgroup analysis: re-recording of all parameters listed here after revascularization intervention

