7.2 Study arms: intervention/control

We do not plan any interventions. The study will examine two study groups in series. First, study group 1 will establish thresholds for hemoglobin values using MSOT. Then, in study group 2, the thresholds will be validated and the specificity and sensitivity will be determined. For a subgroup analysis, some of the IC patients having been included in the study will be reexamined after revascularization intervention.

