### **4.2 Objectives**

#### **Primary objectives**

- Study group 1: Derivation of optimal diagnostic thresholds for hemoglobin-associated MSOT parameters after a heel raise exercise in claudication patients and a healthy control group
- Study group 2: Validation of the diagnostic accuracy of MSOT, employing the cut-off values derived in study group 1, regarding hemoglobin-associated MSOT parameters after a heel raise exercise in claudication patients and a healthy control group in an independent cohort

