## 7 General Considerations

### 7.1 Timing of Analysis

The final analysis will be performed after the last patient entered the study. Study collectives for study group 1 (derivation of thresholds) and study group 2 (validation of thresholds) will be handled separately.

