## 12.5 Samples for PAD II clinical scoring

Parameters	Healthy	PAD II
Angiography TASC score	Value not collected	n (% of total n)
CCDS Morphological flow profile, relevant stenosis PSV	n (% of total n) Mean ±SD	n (% of total n) Mean ±SD
Clinical scoring ABI Absolute/relative walking distance Total walking distance in 6MWT	Mean ±SD	Mean ±SD
Anamnestic scoring Subjectively perceived absolute walking distance Score in VASCUQOL-6 questionnaire	Mean ±SD	Mean ±SD
Hbtot_PRE HbO2_PRE Hb_PRE Difference_ HbO2_Pre/Hb_PRE Oxygen_Saturation_PRE Single_Wavelengths_700nm_PRE - Single_Wavelengths_1300nm_PRE	Mean ±SD	Mean ±SD
Hbtot_Post HbO2_Post Hb_Post Difference HbO2_Post/Hb_Post Oxygen saturation Post Single_Wavelengths_700nm_POST - Single_Wavelengths_1300nm_POST		

Parameters	Sensitivity	Specificity
Angiography TASC score	%	%
CCDS Morphological flow profile, relevant stenosis PSV	%	%
Clinical scoring ABI Absolute/relative walking distance Total walking distance in 6MWT	%	%
Anamnestic scoring Subjectively perceived absolute walking distance Score in VASCUQOL-6 questionnaire	%	%

Hbtot_PRE HbO2_PRE Hb_PRE Difference_ HbO2_Pre/Hb_PRE Oxygen_Saturation_PRE Single_Wavelengths_700nm_PRE - Single_Wavelengths_1300nm_PRE	%	%
Hbtot_Post HbO2_Post Hb_Post Difference HbO2_Post/Hb_Post Oxygen saturation Post Single_Wavelengths_700nm_POST - Single_Wavelengths_1300nm_POST		

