## Severity of stenosis – grouping according to combined TASC subgroups

Parameters	Sensitivity	Specificity
CCDS Morphological flow profile, relevant stenosis PSV	%	%
Clinical scoring ABI Absolute/relative walking distance Total walking distance in 6MWT	%	%
Anamnestic scoring Subjectively perceived absolute walking distance Score in VASCUQOL-6 questionnaire	%	%
Hbtot_PRE HbO2_PRE Hb_PRE Difference_ HbO2_Pre/Hb_PRE Oxygen_Saturation_PRE Single_Wavelengths_700nm_PRE - Single_Wavelengths_1300nm_PRE  Hbtot_Post HbO2_Post Hb_Post Difference HbO2_Post/Hb_Post Oxygen saturation Post Single_Wavelengths_700nm_POST - Single_Wavelengths_1300nm_POST	%	%

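### Does reporting sensitivity and specificity in study group 1, at the Youden cutpoint chosen in the same participants, call for a correction in SAP 9.2?

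*SAP*

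**What the plan says.** SAP 9.2 has two sentences. The first takes the cutpoint from the comparison of healthy volunteers with claudication patients in study group 1 and says the diagnostic properties "will be illustrated by sensitivity and specificity (with 95% confidence interval) associated with a diagnostic test decision dichotomised at that cutpoint". It does not name the group in which these figures are computed. The second reads: "The same cutpoint will be employed in study group 2 for validation of diagnostic properties".

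Four other places give the two groups their roles:
- SAP 4.2 lists as a primary objective for study group 2: "Validation of the diagnostic accuracy of MSOT, employing the cut-off values derived in study group 1", in an independent cohort.
- Protocol 5.1 has the same objective: "Study group 2: Validation of the diagnostic accuracy of MSOT, employing the cut-off values derived in study group 1".
- Protocol 7.2 has group 1 set the thresholds first; after that, "in study group 2, the thresholds will be validated and the specificity and sensitivity will be determined".
- SAP 7.1 states: "Study collectives for study group 1 (derivation of thresholds) and study group 2 (validation of thresholds) will be handled separately".

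The accuracy tables in SAP 12.5 ("Samples for PAD II clinical scoring"), 12.6 and 12.7 each have one sensitivity and one specificity column and no study-group columns. Neither document mentions a bootstrap, cross-validation or any other internal correction.

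**The concern.** A cutpoint that maximises sensitivity plus specificity in a sample partly fits the noise of that sample. Accuracy computed at that cutpoint in the same people is therefore too high on average. Because the second sentence of SAP 9.2 turns to group 2, the first most naturally describes group 1, so such figures will be produced and given ordinary 95% confidence intervals.

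The study aims to raise sensitivity and specificity above those of the preliminary study (SAP 3.2). An overstatement of several points, read as validated accuracy, would bear directly on that claim. Table shells that do not show which group a figure comes from seem to invite that misreading, or even a merging of the two groups.

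**Working it through.** **Inputs.** SAP 6 gives 31 per cell from the AUC calculation (AUC 0.7, significance level 0.05, power 0.8) and about 12 per cell from the t-test. There are four cells: healthy and claudication in each study group. SAP 5.2 plans about 100 participants, which is 100/4 = 25 per cell if split evenly. The 0.7 is a minimum, so AUCs of 0.8 and 0.9 are added as assumptions.

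**The plan's own figure.** One AUC tested against 0.5, equal groups, binormal variance:

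V(AUC) = 0.0099 · exp(−A²/2) · [(5A² + 8) + (A² + 8)], with A = 1.414 · Φ⁻¹(AUC)

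- AUC 0.5: A = 0, so V₀ = 0.0099 × 16 = 0.1584.
- AUC 0.7: A = 0.7415, A² = 0.550, so V₁ = 0.0099 × 0.760 × 19.30 = 0.145.
- n = (1.960·√0.1584 + 0.842·√0.145)² / 0.2² = (0.780 + 0.321)² / 0.04 = 30.3, rounded up to 31.

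This matches the SAP (two-sided). The totals also agree: 4 × 12 = 48 and 4 × 31 = 124.

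**Size of the optimism.** Simulation with 20,000 trials per setting and equal-variance normal readouts separated by d = √2 · Φ⁻¹(AUC). The Youden cutpoint is chosen in n + n participants. The apparent Youden index J = sensitivity + specificity − 1 in those participants is compared with J of the same cutpoint in new participants. Half the difference is the average excess in each measure.

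| AUC | n per cell | J apparent | J in new participants | Excess in J | Excess per measure |
|---|---|---|---|---|---|
| 0.7 | 12 | 0.446 | 0.252 | 0.194 | 10 points |
| 0.7 | 25 | 0.395 | 0.261 | 0.134 | 7 points |
| 0.7 | 31 | 0.384 | 0.263 | 0.121 | 6 points |
| 0.8 | 12 | 0.579 | 0.406 | 0.172 | 9 points |
| 0.8 | 25 | 0.537 | 0.419 | 0.119 | 6 points |
| 0.8 | 31 | 0.527 | 0.422 | 0.105 | 5 points |
| 0.9 | 12 | 0.741 | 0.595 | 0.147 | 7 points |
| 0.9 | 25 | 0.706 | 0.608 | 0.098 | 5 points |
| 0.9 | 31 | 0.698 | 0.610 | 0.088 | 4 points |

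(Differences of 0.001 are rounding.)

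**What group 2 gives.** In a separate run of 8,000 trials at AUC 0.7 and 25 per cell, group 1 shows 0.698/0.698 for sensitivity/specificity. The true values at the chosen cutpoint are 0.631/0.631, and a fresh group 2 of equal size gives 0.629/0.631. The excess is gone, because group 2 played no part in choosing the cutpoint.

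**Intervals in group 1.** At 25 to 31 per cell, exact 95% intervals cover the cutpoint's true sensitivity or specificity 94 to 96% of the time, and Wilson intervals 92 to 95%. For scale, an observed 62% has a Wilson interval of about 43 to 78% at 25 per cell, far wider than the optimism.

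**What a bootstrap would add.** Repeating the cutpoint search in each resample (500 trials, 150 resamples) at AUC 0.7 and 25 per cell gives an average of sensitivity and specificity of 0.695 apparent, 0.650 corrected and 0.633 true. It removes (0.695 − 0.650)/(0.695 − 0.633) = 0.045/0.062, or about 73%. Over AUC 0.7 to 0.9 the share removed is 58 to 61% at 12 per cell and 63 to 78% at 25 to 31.

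**The case for a change.** The best case for a change is that the SAP does not carry its design through to the reporting. SAP 9.2 mentions confidence intervals only in its first sentence. The primary endpoint in SAP 4.3 is the thresholds, and group 2 accuracy is not in the endpoint list. SAP 7.1 foresees one final analysis, with no explicit rule to lock the cutpoint before group 2 is read. The table shells could be filled with figures from either group. The edits would be cheap.

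The observations are accurate, but they do not amount to a gap in the analysis:
- **Intervals.** The diagnostic properties to be validated in the second sentence of SAP 9.2 are those the first sentence has just defined, so reporting them with 95% intervals in group 2 is the ordinary reading.
- **Locking.** SAP 9.2 requires the same cutpoint in group 2, and Protocol 7.2 puts derivation first. Retuning it on group 2 would depart from the plan.
- **Pooling.** No text plans it, and SAP 7.1 points the other way. A sample table without group columns does not override that rule; the natural result is one table per group.
- **Tables 12.6 and 12.7.** These use other targets, with 12.6 "grouping according to combined TASC subgroups" and 12.7 by stenosis on duplex sonography. The cutpoint in SAP 9.2 is tuned to healthy versus claudication, so the simulated excess does not transfer to them. Only 12.5 matches the mechanism.
- **Bootstrap.** It would set a still partly biased figure beside an unbiased one.
- **The smallest size.** The 10-point figure needs 12 per cell, the calculated lower bound, while about 25 per cell is planned. That the re-evaluation comes after 25 + 25 = 50 inclusions, two more than 48, has no bearing on this point.

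One caveat stands. The simulation concerns a single readout, and picking the best of many MSOT readouts would enlarge the excess in group 1. Group 2 still corrects for that if both the readout and its cutpoint are carried over from group 1.

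**Conclusion.** The optimism in the group 1 figures is real: about 4 to 7 points on each of sensitivity and specificity at the planned 25 to 31 per cell, and 7 to 10 at 12 per cell, for one equal-variance binormal readout with an AUC of 0.7 to 0.9. It sits in figures whose role in the plan is derivation. Followed as written, the plan takes its accuracy conclusion from an independent group at an unchanged cutpoint, and that estimate is unbiased.

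What is left is presentation: calling the group 1 values apparent, naming the interval method and showing the 12.5 accuracy table by study group. A competent analyst would do this under SAP 4.2, 7.1 and 9.2 as they stand, and none of it alters the estimate on which the study's claim rests. No change is needed.

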## 10 Reporting Convention

P-values  $\geq 0.001$  will be reported to 3 decimal places; p-values less than 0.001 will be reported as “ $<0.001$ ”. Non-significant P-values ( $>0.05$ ) will be reported to two decimal places. The mean and standard deviation will be reported to one decimal place greater than the original data. Quantiles, such as median, or minimum and maximum will use the same number of decimal places as the original data. Estimated parameters, not on the same scale as raw observations (e.g. regression coefficients) will be reported to three significant figures.

## 11 Technical Details

All analyses are performed using IBM SPSS Statistics, version 24 or newer (IBM Corp., N.Y., USA) and R Statistics, version 3.6 or newer.

## 12 Sample Tables for Data Reporting

### 12.1 Demographic data PAD II patients in study groups 1 and 2

Baseline characteristics-patients with PAD II	
Age	Mean $\pm$ SD
Sex	n (% of total n)
Risk factors Smoking, arterial hypertension, lipid abnormalities, diabetes mellitus, obesity, positive family history	n (% of total n)
Relevant underlying diseases CHD, CHF, atrial fibrillation, CKD, carotid artery stenosis, previous cerebrovascular event	n (% of total n)
Previous vascular surgery/intervention	n (% of total n)
Current Medication	n (% of total n)
Clinical scoring ABI Pulse status lower extremity Fontaine stage, Rutherford stage	Mean $\pm$ SD n (% of total n) n (% of total n)
CCDS Morphological flow profile, Presence of relevant stenosis PSV	n (% of total n) Mean $\pm$ SD
Angiography TASC score	n (% of total n)
MSOT MSOT values for oxygenated/deoxygenated/total hemoglobin, oxygen saturation and single wavelengths from 700nm to 1300nm Difference values ("deltas") between respective MSOT values before and after exercise	Mean $\pm$ SD Mean $\pm$ SD
Walking distances Relative walking distance in 6MWT (until first occurrence of pain) Absolute walking distance in 6MWT (until first stopping because of pain) Total walking distance in 6MWT (total walking distance within the 6 minutes)	Mean $\pm$ SD Mean $\pm$ SD Mean $\pm$ SD
Anamnestic values Subjectively perceived absolute walking distance in everyday life Score in VASCUQOL-6 questionnaire	Mean $\pm$ SD Mean $\pm$ SD

### 12.2 Demographic data healthy volunteers in study groups 1 and 2

Baseline characteristics – healthy volunteers	
Age	Mean $\pm$ SD
Sex	n (% of total n)

Risk factors Smoking, arterial hypertension, lipid abnormalities, diabetes mellitus, obesity, positive familiar history	n (% of total n)
Relevant underlying diseases CHD, CHF, atrial fibrillation, CKD, carotid artery stenosis, previous cerebrovascular event	n (% of total n)
Previous vascular surgery/intervention	n (% of total n)
Current Medication	n (% of total n)
Clinical scoring ABI Pulse status lower extremity Fontaine stage, Rutherford stage	Mean $\pm$ SD n (% of total n) n (% of total n)
CCDS Morphological flow profile, Presence of relevant stenosis PSV	n (% of total n) Mean $\pm$ SD
MSOT MSOT values for oxygenated/deoxygenated/total hemoglobin, oxygen saturation and single wavelengths from 700nm to 1300nm Difference values ("deltas") between respective MSOT values before and after exercise	Mean $\pm$ SD Mean $\pm$ SD
Walking distances Relative walking distance in 6MWT (until first occurrence of pain) Absolute walking distance in 6MWT (until first stopping because of pain) Total walking distance in 6MWT (total walking distance within the 6 minutes)	Mean $\pm$ SD Mean $\pm$ SD Mean $\pm$ SD
Anamnestic values Subjectively perceived absolute walking distance in everyday life Score in VASCUQOL-6 questionnaire	Mean $\pm$ SD Mean $\pm$ SD

### 12.3 Data correlation PAD II patients in study groups 1 and 2

All MSOT parameters have two values: "PRE" means before exercise and "POST" means after exercise. If not explicitly mentioned, the following assumes the analysis of both values.

Parameters	Hbtot	HbO2	Hb	Difference HbO2/Hb	Oxygen saturation	Single wave-lengths from 700nm to 1300nm
Angiography TASC score	Correlation	Correlation	Correlation	Correlation	Correlation	Correlation
CCDS Morphological flow profile, relevant stenosis PSV	Correlation	Correlation	Correlation	Correlation	Correlation	Correlation

Clinical scoring ABI Absolute/relative walking distance Total walking distance in 6MWT	Correlation	Correlation	Correlation	Correlation	Correlation	Correlation
Anamnestic scoring Subjectively perceived absolute walking distance Score in VASCUQOL-6 questionnaire	Correlation	Correlation	Correlation	Correlation	Correlation	Correlation

## 12.4 Data correlation healthy volunteers in study groups 1 and 2

All MSOT parameters have two values: “*Pre*” means before exercise and “*Post*” means after exercise. If not explicitly mentioned, the following assumes the analysis of both values.

Parameters	Hbtot	HbO2	Hb	Difference HbO2/Hb	Oxygen saturation	Single wave-lengths from 700nm to 1300nm
CCDS Morphological flow profile, relevant stenosis PSV	Correlation	Correlation	Correlation	Correlation	Correlation	Correlation
Clinical scoring ABI Absolute/relative walking distance Total walking distance in 6MWT	Correlation	Correlation	Correlation	Correlation	Correlation	Correlation
Anamnestic scoring Subjectively perceived absolute walking distance Score in VASCUQOL-6 questionnaire	Correlation	Correlation	Correlation	Correlation	Correlation	Correlation

## 12.5 Samples for PAD II clinical scoring

Parameters	Healthy	PAD II
Angiography TASC score	Value not collected	n (% of total n)
CCDS Morphological flow profile, relevant stenosis PSV	n (% of total n) Mean ±SD	n (% of total n) Mean ±SD
Clinical scoring ABI Absolute/relative walking distance Total walking distance in 6MWT	Mean ±SD	Mean ±SD
Anamnestic scoring Subjectively perceived absolute walking distance Score in VASCUQOL-6 questionnaire	Mean ±SD	Mean ±SD
Hbtot_PRE HbO2_PRE Hb_PRE Difference_ HbO2_Pre/Hb_PRE Oxygen_Saturation_PRE Single_Wavelengths_700nm_PRE - Single_Wavelengths_1300nm_PRE	Mean ±SD	Mean ±SD
Hbtot_Post HbO2_Post Hb_Post Difference HbO2_Post/Hb_Post Oxygen saturation Post Single_Wavelengths_700nm_POST - Single_Wavelengths_1300nm_POST		

Parameters	Sensitivity	Specificity
Angiography TASC score	%	%
CCDS Morphological flow profile, relevant stenosis PSV	%	%
Clinical scoring ABI Absolute/relative walking distance Total walking distance in 6MWT	%	%
Anamnestic scoring Subjectively perceived absolute walking distance Score in VASCUQOL-6 questionnaire	%	%

Hbtot_PRE HbO2_PRE Hb_PRE Difference_ HbO2_Pre/Hb_PRE Oxygen_Saturation_PRE Single_Wavelengths_700nm_PRE - Single_Wavelengths_1300nm_PRE	%	%
Hbtot_Post HbO2_Post Hb_Post Difference HbO2_Post/Hb_Post Oxygen saturation Post Single_Wavelengths_700nm_POST - Single_Wavelengths_1300nm_POST		

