9.2 Procedures and measurements

After having been fully informed and after having given written consent, all study participants will be asked to provide information on their preexisting conditions, previous operations and current medication. If available, the electronic patient file will be used for this purpose; otherwise, these data will be collected in the anamnesis interview. Particularly interesting are diseases, operations and medication related to the vascular system. Approximately 15 minutes are estimated for information and anamnesis interview.

Furthermore, the subjectively perceived maximum walking distance until the first stopping due to pain in everyday life is to be queried and a questionnaire on the PAD-specific quality of life is to be completed (VASCUQOL-6), which will take about ten minutes.

All other measures will take place in the sonography room in the department of pediatrics, which has been adapted for the use of the MSOT system. Participants will be brought to this room by wheelchair from the department of vascular surgery. It is important that there is no physical exertion during the transport, as this could falsify the measured values. The transport takes about 15 minutes. On site, the participant should lie down on the examination couch and rest for another 15 minutes. Then the first oscillometric measurement of the ankle-brachial index (ABI) is performed. For this purpose, blood pressure cuffs are placed on the participant's arms and legs. The ABI is used in vascular medicine to estimate the severity of PAD. For healthy study participants, the measurement of the ABI is to be regarded as a screening examination. Study participation of healthy volunteers requires normal values in the ABI measurement (the handling of incidental findings in screening is presented in Chapter 13). The oscillometric measurement of the ABI takes only about two minutes. In patients, the measurement of the ABI would also be performed independently of study participation as part of routine diagnostics during the inpatient stay.

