9.3 Recording of target parameters

- Non-invasive MSOT measurements
- Collection of relevant clinical data from patient file
- Recording of the flow profiles of A. femoralis communis and A. poplitea using CCDS
- Recording of ABI before and after exercise
- Recording of the relative (until the first occurrence of pain) and absolute walking distance (until the stopping due to pain)
- Recording of the maximum walking distance in the 6-minute walk test
- Recording of the subjectively perceived maximum walking distance in everyday life
- Recording of the currently perceived PAD-specific quality of life (VASCUQOL-6 questionnaire)
- Recording of the radiological severity of the disease (MRA, CTA, DSA)
[If angiographic imaging is already available due to routine diagnostics independent from this study.]

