***Definition of healthy control group:***

- no PAD previously known
- no diabetes mellitus previously known
- no chronic renal insufficiency previously known
- no symptoms of intermittent claudication
- ABI with values between 0.9 and 1.4 (screening examination before inclusion in the study)
- palpable foot pulses

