**Exclusion Criteria**

- Patients with PAD stage I, III and IV according to Fontaine or categories 0, 4, 5 and 6 according to Rutherford or healthy volunteers with diabetes mellitus, chronic renal failure, claudication symptoms, abnormal ABI or non-palpable foot pulses
- Underage persons
- Lack of written consent
- Safety concerns of the study physician (person with physical, mental or psychiatric conditions which, by the judgement of the study physician, would compromise the person's safety or the quality of the data, thereby rendering the person an ineligible candidate for the study)

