**4 ABI:**

Assessment of ABI value	
no PAD	0.9-1.4
mild PAD	0.75-0.9
moderate PAD	0.5-0.75
severe PAD	<0.5
mediasclerosis	>1.4

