### 7.2 Analysis Population

We will describe all screened and enrolled subjects who fulfil all inclusion criteria and fail all exclusion criteria.

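### SAP table 12.5 asks for a resting-ABI specificity that enrolment can fix at 100% and a TASC specificity that cannot be estimated; part of table 12.6 is circular for unimaged volunteers

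*SAP*

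**What the plan says.** **Table 12.5.** The first part compares Healthy with PAD II. The second part has percentage cells for sensitivity and specificity of TASC, CCDS, the row "Clinical scoring ABI Absolute/relative walking distance Total walking distance in 6MWT", the anamnestic scores and the MSOT parameters. In the first part, the TASC cell for healthy participants is marked as not collected.

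**ABI as an entry test.** The SAP's definition of the control group requires "ABI with values between 0.9 and 1.4 (screening examination before inclusion in the study"), and its exclusion criteria remove volunteers with "abnormal ABI or non-palpable foot pulses". Protocol 9.2 makes the study's first resting measurement the screening test: "For healthy study participants, the measurement of the ABI is to be regarded as a screening examination". SAP 7.2 limits the analysis population to subjects "who fulfil all inclusion criteria and fail all exclusion criteria".

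**ABI bands and time points.** In SAP 5.4, the table headed "Assessment of ABI value" gives 0.9-1.4 as no PAD, 0.75-0.9 as mild PAD and values above 1.4 as mediasclerosis. Nothing names these bands as the test threshold for section 12. Protocol 9.3 lists "Recording of ABI before and after exercise", but the ABI row does not say which value it means. The note in SAP 12.3 and 12.4 about two values covers MSOT parameters only, and the Youden rule in SAP 9.2 covers MSOT values only.

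**Table 12.6.** Accuracy is tabulated against combined TASC subgroups. SAP 5.4 defines three of these (aTASC 1 to 3), whereas the first part of 12.6 has four columns, I to IV. The second part names no contrast. Volunteers without angiography are placed in aTASC 1 when history, ABI and CCDS are normal. People with unremarkable imaging at all three levels are also aTASC 1.

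**The concern.** A specificity is informative only if a control could have tested positive. In table 12.5 the resting ABI decides who becomes a control, and the SAP's own normal band repeats the entry limits. The TASC row asks for a specificity where no control has a TASC value. In table 12.6, ABI and CCDS help to define the healthy class for unimaged volunteers and may then be scored against it.

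The missing time point decides which quantity is reported: the resting value can be fixed by entry, the post-exercise value is not. Two analysts following the SAP could put different quantities in the same cell. At stake is a reader taking a specificity of 100% as evidence about ABI, TASC or CCDS when it reflects admission or class assignment. These figures stand beside those of MSOT, which protocol section 2 presents as closing a gap left by ABI and CCDS.

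**Working it through.** **1. Group sizes (SAP 6).** Four groups of 12 give 4 × 12 = 48; four groups of 31 give 4 × 31 = 124. The plan's total of about 100 gives 100 / 4 = 25. The 31 can be reproduced for an AUC of 0.7, two-sided 5%, power 0.8, assuming a null AUC of 0.5 (not stated). With the Obuchowski variance V = 0.0099·exp(−A²/2)·[(5A²+8)+(A²+8)], A = 0 under the null and A = 1.414·z(0.7) = 0.74 under the alternative, V₀ = 0.158 and V₁ = 0.145. Then n = (1.96√V₀ + 0.842√V₁)² / 0.2² = 30.29, rounded up to 31. SAP 7.1 handles the two study groups separately, so the control count per table is 12, 25 or 31.

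**2. Resting ABI at 0.9-1.4, table 12.5.** Every admitted volunteer has a resting ABI in this band, and the entry value is the study value. If the band is read as test-negative and 0.9 counts as normal (the SAP puts 0.9 in two bands), false positives = 0 and specificity = n/n. The exact 95% lower limit is 0.025^(1/n):

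| Controls | Specificity | Exact 95% CI |
|---|---|---|
| 12 | 12/12 | 73.5-100% |
| 25 | 25/25 | 86.3-100% |
| 31 | 31/31 | 88.8-100% |

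These intervals look like estimates, but the numerator was never free. Without selection, 31/31 would have probability s³¹ for true specificity s: 0.95³¹ = 20%, 0.90³¹ = 3.8%, 0.80³¹ = 0.1% (the values of s are assumptions).

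**3. Resting ABI at a cut above 0.9.** Let s be the unselected specificity, a the share of otherwise eligible volunteers with ABI 0.9-1.4, and p the share above 1.4. If values above 1.4 count as positive, reported specificity is s/a. If only low values count as positive, it is (s − p)/a. With assumed s = 80% and a = 90%:

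- values above 1.4 count as positive, or nobody is above 1.4: 80/90 = 88.9%;
- only low ABI positive, exclusions split evenly (p = 5%): 75/90 = 83.3%;
- only low ABI positive, all exclusions above 1.4 (p = 10%): 70/90 = 77.8%.

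Selection still acts, but its size and even its direction depend on a rule that the SAP does not give.

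**4. Cells that stay free in 12.5.** Post-exercise ABI is not an entry criterion. ABI sensitivity is free because patients enter on Fontaine or Rutherford stage. CCDS is not an entry criterion, so its specificity here is not fixed.

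**5. TASC in 12.5.** With no TASC value in volunteers, the denominator of specificity is empty. If the aTASC 1 default fills it, each volunteer so assigned is negative by definition and the result is 100%.

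**6. Table 12.6.** An unimaged volunteer is aTASC 1 only with normal ABI and CCDS. One with an abnormal CCDS is not covered by the default, so a false-positive CCDS stenosis reading cannot occur among default-assigned volunteers. The same holds for resting ABI. It does not hold for imaged aTASC 1 participants, for PSV (no limit is stated), for post-exercise ABI, or for the MSOT rows, since MSOT is not part of the class definition.

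**The case against.** These are sample tables. No objective or endpoint concerns comparator accuracy, no test of MSOT against ABI is planned, and the n/n result needs the 0.9-1.4 band, which nothing designates as the threshold. The entry rule is plainly stated, so an informed reader could discount the figure. The small consequence stands. The rest does not remove the point: the SAP commits in 8.3 to analysis as written, 0.9-1.4 is its only no-PAD band, and the TASC specificity cell fails at any threshold.

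Three stronger readings are tempting.

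- A reader might infer that selection inflates ABI specificity at every cut. Step 3 shows that this depends on how values above 1.4 are classed.
- A reader might infer that all ABI and CCDS accuracy in table 12.6 is circular, so that the table should be confined to imaged patients. The circularity reaches only unimaged volunteers and the two readings that define their class. Confining the table would also discard a non-circular contrast for MSOT and replace diseased versus healthy with aTASC 2 versus 3, which no objective asks for.
- A reader might infer that removing the TASC accuracy row loses nothing because an n (%) cell already exists. That cell uses total n, while imaging is optional, so the denominator needs changing.

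**Conclusion.** The point holds, at minor severity. At the SAP's no-PAD band, resting-ABI specificity in table 12.5 is n/n by selection: 31/31 (88.8-100%) at the largest planned size and 12/12 (73.5-100%) at the smallest. This assumes that the entry rule is followed, that the first resting ABI is the value tabulated, and that 0.9 counts as normal. TASC specificity in 12.5 is not estimable, or is 100% by assignment. In 12.6, resting-ABI and CCDS relevant-stenosis specificity cannot be interpreted where unimaged volunteers form the reference class; whether they do is not stated.

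The harm is a misleading comparator display. It would be wrong to infer that MSOT accuracy is compromised: the cut-point derivation and validation in SAP 9.2 use neither ABI, TASC nor CCDS as a test. The missing ABI time point and cut-point would alone be only missing detail. They matter here because one reading gives a forced result and another a real estimate.

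**What to change.** **Table 12.5.** Split ABI into resting and post-exercise rows, each with a stated cut-point, including how 0.9 and values above 1.4 are classed. Mark resting-ABI specificity as fixed by the enrolment criteria and not estimable. Keep ABI sensitivity. Remove the TASC accuracy row and report TASC findings as n/N of imaged patients.

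**Table 12.6.** Match the columns to the three aTASC classes and state the contrast used for sensitivity and specificity. Keep the MSOT rows. Mark the resting-ABI and CCDS relevant-stenosis specificity cells as not interpretable wherever unimaged volunteers form the reference class.

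**Table 12.7.** Apply the same ABI time-point and cut-point labelling.

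**Cost.** Table edits only; no new data and no change to the primary analysis. An imaged-patients-only analysis may be added to 12.6, labelled exploratory. Its size is unknown, because angiography is used only if already available and less than 12 months old. If all 31 patients of one study group were imaged and 40% were aTASC 3 (both assumed), 31 × 0.4 gives about 12 patients, and an observed 10/12 would have an exact 95% CI of 51.6-97.9%.
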